## **Study design and participants**

We conducted a retrospective analysis of prospectively collected data on a cohort of patients undergoing HBOT at the University Health Network's Hyperbaric Medicine Unit in Toronto, ON, Canada, between February 2016 and June 2021. All studied patients provided written consent to undergo HBOT (for a variety of clinical indications), and were scheduled to receive at least ten cycles of treatment at our large referral center during this timeframe. Patients underwent PFT assessment before starting HBOT and following every 20 treatment sessions thereafter.

Research ethics approval for the analysis of these data was provided by the University Health Network (Toronto, ON) Research Ethics Board (CAPCR ID: 19-5081.1). Data were collected retrospectively from the electronic records of enrolled patients, and comprised demographic information, HBOT indication and protocol, treatment complications, and PFT results immediately before the first HBOT session and following every subsequent 20 treatments. The protocol was retrospectively registered during the data collection stage and prior to analysis on Clinicaltrials.gov (trial ID: NCT05088772). We followed the STROBE guidelines for reporting observational cohort studies (S2 Table) [11].

## **Hyperbaric oxygen therapy protocol**

The HBOT protocol utilized at our center has been previously described [12]. HBOT was performed with 100% O2 at a pressure of 2.4 or 2.0 ATA (243 or 203 kPa) for 90 minutes, with 1-2 air breaks (0.21 fraction of inspired O2 at the same ATA) per session, five times weekly in one of three mono-place chambers (Sechrist 3600H and Sechrist 4100H, Sechrist Industries Inc.,

Anaheim, CA, USA; PAH-S1-3200, Pan-America Hyperbarics Inc., Plano, TX, USA) or through a plastic hood in a multi-place chamber (rectangular Hyperbaric System, Fink Engineering PTY-LTD, Warana, Australia).

### **Pulmonary function testing protocol**

Bedside spirometry was performed by a trained respiratory therapist using a KoKo Trek USB Spirometer software and pneumotachometer (KoKo, USA). Pulmonary function tests were completed at the time of consultation (prior to the first HBOT treatment) and following every 20 treatments thereafter. In rare cases when PFTs could not be obtained on the exact date of a 20th, 40th, or 60th treatment (e.g., due to equipment limitations), they were obtained on the nearest possible date of another treatment and rounded to an increment of 20 at the time of data analysis. The spirometry equipment was calibrated at the beginning of each day. Patients were tested in a seated position with nose clips, in accordance with American Thoracic Society testing criteria [13], and results were compared against Knudson reference values [14] to determine their percentage of predicted values based on age, sex, and height. To capture potential restrictive, obstructive, and effort-independent changes, three markers of dynamic lung function were recorded: FEV1% (percentage of predicted FEV1), FVC% (percentage of predicted FVC), and FEF25-75% (percentage of predicted FEF25-75). The data utilized in this study comprise the highest readings for each of these variables from three satisfactory forced expiratory maneuvers performed as part of each PFT assessment. The primary outcome of this study was change in spirometry performance over the course of HBOT. We additionally classified the degree of any baseline PFT abnormalities on the basis of each independent parameter's deviation from the

predicted value, designating mild abnormality as 70-79%, moderate abnormality as 60-69%, and severe abnormality as less than 60%.

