### **Data collection and statistical analysis**

Patient demographic data and past medical history characteristics were summarized using descriptive statistics, and continuous data were expressed as means  $\pm$  standard deviations. Linear mixed effect regression models were used to estimate the adjusted sample mean scores of PFT outcomes FEV1%, FVC%, and FEF25-75% at each timepoint for the cohort. Timepoint was included as the fixed effect and individual subject as the random effect for each outcome for the overall cohort. PFT outcomes were also modeled for subgroups by timepoint interaction for pre-existing respiratory disease, smoking status, and treatment pressure (in ATA). Similarly, individual subjects were included as random effects. The maximum likelihood estimation was used to prepare the mixed models and analyzed under the intention-to-treat principal. Post-hoc pairwise comparisons between timepoints were conducted for each grouping of pre-existing respiratory disease, smoking status, and treatment pressure, for each PFT variable. Pairwise comparisons were adjusted using Tukey's HSD. The alpha was set to 0.05. All analyses were performed using R version 4.0.3.

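### FEF25-75 is taken as its own highest value over three blows, which tends to favour a less complete blow and can bias its level and its change over time

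*Combined protocol and SAP*

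**What the plan says.** All from the combined protocol and SAP.

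- **Selection rule** (Pulmonary function testing protocol): the analysed data "comprise the highest readings for each of these variables from three satisfactory forced expiratory maneuvers". Each variable takes its own maximum. Nothing ties FEF25-75 to the blow that supplied the FVC, or to any single best blow.
- **Role of the markers** (same section): "To capture potential restrictive, obstructive, and effort-independent changes, three markers of dynamic lung function were recorded". FEF25-75% is one of the three, beside FEV1% and FVC%, and "The primary outcome of this study was change in spirometry performance over the course of HBOT". Baseline values of each marker are also graded in 10-point bands below 80% of predicted.
- **Safeguards** (same section): "Bedside spirometry was performed by a trained respiratory therapist", and testing was "in accordance with American Thoracic Society testing criteria". No numeric limit for completeness or repeatability is given.
- **Repeat testing** (Study design and participants): "Patients underwent PFT assessment before starting HBOT and following every 20 treatment sessions thereafter".
- **Model** (Data collection and statistical analysis): "Timepoint was included as the fixed effect and individual subject as the random effect for each outcome for the overall cohort". There is no term for FVC, expiratory time or test quality.

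**The concern.** For FEV1 and FVC, a higher reading means a better blow, so taking the maximum is sensible. FEF25-75 behaves differently. Its measuring window is the middle half of the volume exhaled in that same blow. If the patient stops early, the recorded FVC shrinks, the window slides to an earlier and faster part of the blow, and the reading rises. A maximum taken without regard to FVC therefore leans towards the shorter of the eligible blows.

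Two things are at stake. First, baseline FEF25-75% is pushed upward, and its abnormality grade with it. Second, if blows are more or less complete at later visits than at baseline, the upward push differs between visits and appears as change over treatment, which is the primary outcome. A subject-level random effect removes a bias that is constant across a patient's visits, but not one that varies with the visit.

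**Working it through.** The documents give no FEF25-75 values, SD, sample size or data on blow completeness, so there is no stated figure to reproduce. Apart from the selection rule and the grading bands, every input below is an assumption.

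**1. Effect of stopping early.** Assume exponential emptying, V(t) = F(1 − exp(−t/τ)), stopped at fraction c of the full volume F. The recorded FVC is cF, and the time to exhale a fraction p of it is −τ ln(1 − pc). Hence

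FEF25-75(c) = 0.5cF / {τ [ln(1 − 0.25c) − ln(1 − 0.75c)]}

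F and τ cancel in the ratio to a complete blow:

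- c = 1: 0.5 / ln(0.75/0.25) = 0.5/1.0986 = 0.4551
- c = 0.95: 0.475 / ln(0.7625/0.2875) = 0.475/0.9754 = 0.4870
- Ratio: 0.4870/0.4551 = 1.070, so the blow reads 7.0% high.

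The second model below adds a slow tail (60% of volume at time constant 0.4 s, 40% at 2.0 s).

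| Shortfall | Single exponential | Slow tail |
|---|---|---|
| 1% | +1.4% | +2.8% |
| 2% | +2.8% | +5.5% |
| 3% | +4.2% | +8.3% |
| 5% | +7.0% | +13.8% |
| 10% | +13.8% | +27.3% |

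The slow tail roughly doubles the effect (13.8/7.0 ≈ 2.0). The bias could therefore differ between patients with and without prior lung disease, a split the plan models by timepoint.

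**2. Which blow the maximum picks.** Sessions of three blows were simulated (200,000 per setting) with single-exponential emptying. If blows differ only in completeness, the maximum always comes from the least complete one. Once flow rate or starting volume also varies between blows, this happens in about 40-80% of sessions, depending on the setting. Chance is 1/3 = 33%.

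**3. Baseline level.** At a mean shortfall of 4%, FEF25-75 relative to a complete blow of average flow was +10.4% under the maximum rule against +2.4% from the blow with the largest FEV1 + FVC in one setting, and +11.3% against +7.1% in another. For the grading bands, a 7% inflation turns 75% into 75 × 1.07 = 80.3% (mild to not abnormal) and 66% into 66 × 1.07 = 70.6% (moderate to mild). This needs no change in technique between visits.

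**4. Change between visits, true lung function unchanged, mean shortfall improving from 4% to 2%.**

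| Assumed variation | Maximum rule | Best blow |
|---|---|---|
| Exponentially distributed shortfall, 2% variation in time constant | −4.2% | −0.6% |
| Uniform shortfall, 5% variation in time constant, 2% in volume | −3.1% | −1.4% |
| Range over settings | about −2.9% to −4.2% | about −0.4% to −1.4% |

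At an illustrative 80% of predicted, the maximum-rule range is 80 × 0.029 = 2.3 to 80 × 0.042 = 3.4 percentage points.

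A wider grid took completeness from uniform on 0.95-1, 0.93-1 or 0.90-1 at baseline to 0.98-1 at follow-up. The maximum rule gave −2.2% to −7.5% and the best blow +0.3% to −3.0%. The best blow reduces the bias but does not always remove it.

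**5. No change in completeness.** The bias is then the same at each visit, and this mechanism produces no false change.

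**The case against.** A reader might infer that the rule simply selects the least complete blow and so manufactures a decline as patients get better at the test. The documents do not support that, for these reasons:

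- **Eligibility is limited.** Blows had to be satisfactory, made under a therapist's supervision and tested to a cited standard. That restricts how short an eligible blow can be. It does not dispose of the point, because no numeric limit is stated and shortfalls of 1-3% already move the reading by 1.4% to 4.2%. What the standard says about choosing FEF25-75 cannot be seen from the documents.
- **Selection is a tendency.** Ordinary variation in effort and volume often makes another blow the highest.
- **The direction is open.** Nothing in the documents reports completeness or technique over time. If practice also raised flow by 3%, the 4%-to-2% case would become 1.03 × 0.957 = 0.986, or −1.4%; with 5% it would be 1.05 × 0.957 = 1.005, or +0.5% (using −4.3%, from a repeat simulation of the first setting).
- **The size depends on the assumed shape of the shortfall.** The exponential setting puts about 8% of baseline blows more than 10% short, and some of those might not pass as satisfactory. Uniform shortfall with the same mean gives −3.5% in place of −4.2%.
- **The best blow is not always closer to the truth.** In the 5% flow-gain case it shows 1.05 × 0.994 = 1.044, or +4.4%, against +0.5% for the current rule. That does not defend the current rule, which looks better there only because two technique artefacts happen to offset.
- **Feasibility is unknown.** Data came retrospectively from electronic records, and nothing says individual blows were kept. This stands, and it shapes the fix.

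**Conclusion.** The point holds as a weakness in how one marker is selected. The plan's rule takes FEF25-75 as an unlinked maximum. That tends to favour a less complete blow, inflates baseline FEF25-75% and its grading, and biases change over time if completeness differs between visits. Under the assumed models, an improvement in mean shortfall from 4% to 2% gives a spurious change of about −2.9% to −4.2%, against −0.4% to −1.4% from the best blow. It gives none if completeness is stable.

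These sizes rest on assumed emptying curves, shortfall distributions and blow-to-blow variation. The grading concern also assumes that the reference values describe complete blows. Neither the sign nor the size of any bias in this cohort can be determined from the documents, so it would be wrong to conclude that an observed fall in FEF25-75% is spurious. Nor does the point carry over to FEV1% or FVC%, or undermine the primary outcome as a whole. It is a cheap improvement affecting FEF25-75% only.

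**What to change.** - Keep the highest FEV1 and the highest FVC as now.
- Where individual blows were stored, take FEF25-75 from the single satisfactory maneuver with the largest FEV1 + FVC, at every visit. Report the current maximum rule alongside.
- Where only summary values exist for a patient at any visit, keep the current rule for all of that patient's visits, so that rules are not mixed within a patient. Flag those tests and interpret FEF25-75% change with that caveat.
- State the rule explicitly in the Pulmonary function testing protocol.

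Cost: re-extracting stored maneuvers, one wording change and a second run of the FEF25-75% model. Some tests may have no blow-level data. If none were kept, what remains is a stated limitation on FEF25-75%.

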### **Data collection and statistical analysis**

Patient demographic data and past medical history characteristics were summarized using descriptive statistics, and continuous data were expressed as means  $\pm$  standard deviations. Linear mixed effect regression models were used to estimate the adjusted sample mean scores of PFT outcomes FEV1%, FVC%, and FEF25-75% at each timepoint for the cohort. Timepoint was included as the fixed effect and individual subject as the random effect for each outcome for the overall cohort. PFT outcomes were also modeled for subgroups by timepoint interaction for pre-existing respiratory disease, smoking status, and treatment pressure (in ATA). Similarly, individual subjects were included as random effects. The maximum likelihood estimation was used to prepare the mixed models and analyzed under the intention-to-treat principal. Post-hoc pairwise comparisons between timepoints were conducted for each grouping of pre-existing respiratory disease, smoking status, and treatment pressure, for each PFT variable. Pairwise comparisons were adjusted using Tukey's HSD. The alpha was set to 0.05. All analyses were performed using R version 4.0.3.

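### The pressure-by-timepoint result is unadjusted for indication in a non-randomised cohort: label it so, tabulate covariates by pressure and, where groups overlap, add one supporting adjusted model

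*Combined protocol and SAP*

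**What the plan says.** Under Study design and participants, the cohort is mixed: "All studied patients provided written consent to undergo HBOT (for a variety of clinical indications". The records collected "comprised demographic information, HBOT indication and protocol, treatment complications", so indication is in the dataset. Eligibility asks only that patients were "scheduled to receive at least ten cycles of treatment at our large referral center during this timeframe", so not everyone need reach the tests at sessions 20, 40 and 60.

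The Hyperbaric oxygen therapy protocol section gives treatment "at a pressure of 2.4 or 2.0 ATA (243 or 203 kPa) for 90 minutes", with one or two air breaks and a mono-place or multi-place chamber. It does not say how a patient came to receive one pressure or the other. It defers to a reference: "The HBOT protocol utilized at our center has been previously described [12".

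The Pulmonary function testing protocol section expresses each result as a "percentage of predicted values based on age, sex, and height".

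Under Data collection and statistical analysis, the overall model has timepoint as fixed effect and subject as random effect. Then: "PFT outcomes were also modeled for subgroups by timepoint interaction for pre-existing respiratory disease, smoking status, and treatment pressure (in ATA". No covariate is listed for these models, and it is not said whether the three factors enter one model or three. The follow-up contrasts are within group: "Post-hoc pairwise comparisons between timepoints were conducted for each grouping of pre-existing respiratory disease, smoking status, and treatment pressure". The section calls its model means adjusted but lists nothing they are adjusted for. Its only other use of the word refers to Tukey's multiplicity method. Descriptive summaries are planned, but not by pressure.

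**The concern.** A pressure-by-timepoint interaction estimates whether lung function changes differently at 2.4 and 2.0 ATA. In a non-randomised cohort with mixed indications, patients at the two pressures may also differ in why they were treated, in smoking and in lung disease. If any of these affects the change in spirometry, the interaction can show a difference that pressure did not cause, or hide one that it did. The plan calls for no table that would let a reader judge this, and its use of the word adjusted could suggest that the matter has been handled. What is at stake is how one subgroup result is read.

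**Working it through.** The documents give no sample size, SD, pressure split or indication mix, so there is no planned figure to reproduce. Every input below is assumed except the visit schedule (baseline and sessions 20, 40 and 60) and alpha of 0.05.

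**1. Size of the bias.** Let a covariate's prevalence differ by *d* between pressures, and let patients with it change by δ points more. With no true pressure effect, the unadjusted contrast is shifted by *d* × δ. It is zero if either is zero. Otherwise: 0.3 × 1 = 0.3; 0.7 × 1 = 0.7; 0.3 × 3 = 0.9; 0.7 × 3 = 2.1 percent-predicted points.

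**2. Do percent-predicted scaling and the random subject effect remove it?** They deal with differences in level, not in change. Check: 4,000 simulated patients, two timepoints, prevalence 0.7 against 0.3, 5 points of extra decline, no true pressure effect. The expected shift is −0.4 × 5 = −2.0. Estimated interaction:
- no covariate: −2.0 (SE 0.26)
- covariate as main effect only: −2.0 (SE 0.26)
- covariate-by-time term added: −0.19 (SE 0.27)

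Only the covariate-by-time term helps.

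**3. False-positive rate and error at session 40.** Simulation with 2,000 runs per setting: 100 patients, attendance 100/100/60/20% (full attendance at session 20 is generous given the eligibility rule), subject SD 14, residual SD 6, pressures split 50:50, three indication classes, smoking 30%, lung disease 20%, covariate effect linear in session number, true pressure effect zero. The unadjusted model has 4 × 2 = 8 fixed parameters. The adjusted model adds a main effect and a linear time term for each of four covariate columns: 8 + 2 × 4 = 16 (18 with four indication classes). These counts take smoking as two-level, which the plan does not state.

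| *d* × δ | Unadjusted: bias; false positives; RMSE | Adjusted: bias; false positives; RMSE |
|---|---|---|
| 0.3 × 1 | −0.28; 5.2%; 2.13 | 0.01; 5.0%; 2.21 |
| 0.7 × 1 | −0.74; 6.4%; 2.22 | −0.08; 5.2%; 2.82 |
| 0.3 × 3 | −0.88; 7.0%; 2.28 | 0.02; 5.1%; 2.20 |
| 0.7 × 3 | −2.18; 18.8%; 3.05 | −0.08; 4.5%; 2.79 |

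With *d* = 0 the unadjusted rate is about 5% and the adjusted rate 4.6% to 5.9%. Repeat runs gave about 17% to 20% unadjusted in the last row and about 4% to 6% adjusted.

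**4. Other assumed inputs.** In a two-timepoint version (SD of change 8, *d* 0.2 to 0.6, δ 3 to 5, 50 to 200 patients) the unadjusted rate runs from about 7% to 72%. The answer depends almost wholly on the covariate-by-pressure table.

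**5. Cost in precision.** For one two-class covariate the SE ratio is 1/√(1 − *d*²): 1.05 at 0.3 and 1.40 at 0.7. In the simulation the SE goes from about 2.08 unadjusted to 2.20 at *d* = 0.3 (5% to 6% more), 2.81 at 0.7 (2.81/2.08 = 1.35) and 4.92 at 0.9 (2.4-fold).

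**6. If the covariate effect is not linear.** Suppose it is complete by session 20, at 0.7 × 3. Linear time terms then leave a bias of −1.1 at session 20, against −2.1 unadjusted, with a false-positive rate of about 9% to 10% against 23.1%. Bias is about zero at session 40. At session 60 it is about +0.9 to +1.0, an overcorrection, and RMSE is about 4.7 to 4.8 against 4.0 to 4.1 unadjusted. The 4% to 6% in step 3 therefore applies to session 40 with a linear effect.

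**7. Fully categorical time terms.** These need 4 × 6 = 24 parameters. The model could not be estimated in 3% to 8% of runs at *d* up to 0.7, in 38% at *d* = 0.9, and in 35% with 60 patients at *d* = 0.7.

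**The case against.** The plan states no inference between pressures. Its post-hoc contrasts compare timepoints within each pressure, the Objectives section contains no comparison of pressures, and nothing in the documents attributes an effect to pressure. This stands, and it makes the matter mainly one of labelling. It does not remove the point, because the interaction is modelled and can be read as an effect of pressure.

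Confounding is not shown. A reader might infer that pressure was chosen by indication and that the comparison is therefore biased. The documents do not say how it was chosen and defer the treatment protocol to a reference not available here. Separate fitting of the three factors is also an inference. If they are fitted jointly, smoking and respiratory disease are in the model, and how far they are adjusted for depends on their time terms. Indication is omitted on either reading.

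Adjustment may not help. RMSE rises in two of the four confounded settings. For an assumed true difference of 5 points, power falls from about 67% (5/2.08 = 2.40 SEs) to about 43% (5/2.81 = 1.78). Where indication nearly determines pressure, the two cannot be separated. This stands, and is why the model should depend on the table and sit beside the planned result.

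Chamber type and air breaks may also differ by pressure. They belong in the table, and an adjusted result should list what it adjusts for.

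**Conclusion.** The point holds as an optional improvement to a subgroup analysis. The pressure-by-timepoint result is unadjusted for indication, and for smoking and respiratory disease if the factors are fitted separately. Neither percent-predicted scaling nor the random subject effect changes that for differences in change over time.

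The size in this cohort is unknown. On the four-timepoint assumptions above, with effects up to 3 points, the excess of false positives at session 40 is small except at a mix difference of 0.7 with a 3-point effect. Larger assumed effects give larger rates.

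Two stronger readings are not supported. One is that the study's main result is compromised: whole-cohort change and within-pressure change do not depend on comparing pressures. The other is that an adjusted model would yield the effect of pressure: it addresses only the covariates included, and linear time terms can leave or even reverse part of the bias at sessions 20 and 60.

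**What to change.** 1. State whether the three factors are fitted separately or jointly. Label the pressure-by-time result unadjusted and descriptive. Tabulate indication, smoking, respiratory disease, chamber type and number of air breaks by pressure.
2. Where that table shows overlap and adequate numbers, add one supporting mixed model for each PFT variable: random subject effect, timepoint by pressure, and covariate-by-time terms for respiratory disease, smoking and a broad indication group. Main effects alone are not enough. Terms linear in session number save parameters, but the report should say that they assume a steady effect. Use categorical terms only where numbers allow.
3. Report the adjusted pressure-by-time contrast with its 95% CI beside the unadjusted one, name the covariates, and say where it cannot be estimated.

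The cost is some wording, one table and one extra model per outcome. Indication is already collected; chamber type and air breaks should be confirmed as recorded per patient. The adjusted interval will be wider, and when confounding is weak its total error can exceed that of the unadjusted result.

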### **Objectives**

The primary objective of this study was to evaluate changes in series of pulmonary function tests (PFTs) performed over the course of recurrent HBOT exposures. A secondary study outcome was the incidence of pulmonary complications such as lung barotrauma.

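### Subgroup-by-timepoint interactions are fitted, but the only subgroup comparisons stated are within-group contrasts over time; no interaction test or between-group difference in change is stated

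*Combined protocol and SAP*

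**What the plan says.** All the relevant text on subgroups is in the section on data collection and statistical analysis. After the overall-cohort mixed model, it states: "PFT outcomes were also modeled for subgroups by timepoint interaction for pre-existing respiratory disease, smoking status, and treatment pressure (in ATA"). The comparisons drawn from these models are then given as: "Post-hoc pairwise comparisons between timepoints were conducted for each grouping of pre-existing respiratory disease, smoking status, and treatment pressure, for each PFT variable". Two further sentences govern them: "Pairwise comparisons were adjusted using Tukey's HSD" and "The alpha was set to 0.05".

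No section states an F, Wald or likelihood-ratio test of the interaction, or a between-group difference in change with an interval. The Objectives section gives the primary aim as to "evaluate changes in series of pulmonary function tests (PFTs) performed over the course of recurrent HBOT exposures". It names pulmonary complications as a secondary outcome and states no subgroup objective.

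**The concern.** An interaction term lets the course over time differ by group, so fitting one suggests some interest in whether it does. The contrasts that follow ask a different question: in this group, did lung function change between two timepoints? Tukey adjustment controls error over those pairwise comparisons. It does not turn a within-group contrast into a between-group one.

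If results are reported only in this form, readers will tend to set the groups side by side and compare significance. That can mislead in two directions. A change significant in one group and not in the other may be taken as a difference when there is none. A non-significant change in a small group, for instance patients with lung disease, may be taken as reassurance when it reflects low power. A difference in significance is not evidence of a difference in change.

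**Working it through.** The plan gives no sample size, SD, effect size or power, so there is no figure of its own to reproduce. The check is of what the stated contrasts estimate, followed by an illustration under assumptions.

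**1. What the contrasts estimate.** Take two groups A and B, with baseline and A as reference levels. At timepoint *t*:
- change from baseline in A = β_t
- change from baseline in B = β_t + δ_t
- difference in change, B minus A = δ_t, the interaction coefficient

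The stated comparisons test β_t = 0 and β_t + δ_t = 0 (and the contrasts between later timepoints). None tests δ_t = 0. The δ_t are nevertheless in the fitted model.

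**2. How many contrasts.** The spirometry section refers to tests "on the exact date of a 20 th , 40 th , or 60 th treatment". With baseline that makes 4 timepoints, so 4 × 3 / 2 = 6 contrasts per group and outcome. There are three PFT variables and three factors. Pressure has two levels ("at a pressure of 2.4 or 2.0 ATA (243 or 203 kPa) for 90 minutes"); two levels are assumed for the other factors. That gives 3 × (2 + 2 + 2) = 18 families and 18 × 6 = 108 contrasts, none of them between groups.

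**3. Illustration: equal true change, discordant significance.** Assumptions: two independent groups with the same true change, normal approximation, known variance, complete data, Tukey applied over four timepoints within each group, and one contrast (baseline against 60 sessions).
- Critical value: q/√2 = 2.569 (per-contrast two-sided alpha 0.0102).
- Larger group at 80% power: noncentrality = 2.569 + 0.842 = 3.411.
- Smaller group: noncentrality = 3.411 × √(n_small/n_large).
- P(exactly one significant) = p₁(1 − p₂) + p₂(1 − p₁).

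| Split | Power, smaller group | P(exactly one significant) |
|---|---|---|
| 50/50 | 0.800 | 0.8 × 0.2 + 0.8 × 0.2 = 0.320 |
| 30/70 | 0.368 | 0.8 × 0.632 + 0.368 × 0.2 = 0.579 |
| 20/80 | 0.194 | 0.8 × 0.806 + 0.194 × 0.2 = 0.684 |

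A direct between-group test of the same contrast rejects in 5% of cases at 1.96, or 1% at 2.569, whatever the split. A simulation with 400,000 runs per cell agreed.

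**4. Sensitivity to the assumed power.**

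| Power, larger group | 50/50 | 30/70 | 20/80 |
|---|---|---|---|
| 20% | 0.320 | 0.245 | 0.227 |
| 50% | 0.500 | 0.500 | 0.500 |
| 60% | 0.480 | 0.553 | 0.575 |
| 80% | 0.320 | 0.579 | 0.684 |
| 95% | 0.095 | 0.432 | 0.660 |

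Unequal groups raise the figure only when the larger group's power is above 50%; below that they lower it. With no true change in either group the figure is 2 × 0.0102 × 0.9898 = 0.020 for one contrast, and about 0.095 for having any significant result among the six.

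**5. Multiplicity of the remedy.** Three factors by three PFT variables give nine interaction tests. Unadjusted and treated as independent, the chance of at least one false positive is 1 − 0.95⁹ = 0.370.

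**The case against.** The strongest reply is that the plan already contains the right analysis. With timepoint categorical, the interaction coefficients are the between-group differences in change, and the joint test comes from the same fit. The section is a short past-tense methods paragraph, and post-hoc comparisons under a general alpha are compatible with an omnibus test that was run but not mentioned. This stands as far as it goes: a reader might infer that no interaction test was done, or that the models could not address subgroup differences, and the documents support neither. They show only that no such test or contrast is stated, and the label post-hoc does not supply one.

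The second reply is that no stated objective is harmed. Describing change separately by group is a legitimate aim, the Objectives ask for no subgroup comparison, and the documents draw no conclusion that subgroups differ. That also stands. The harm is conditional on within-group significance being used to compare groups.

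The third reply is that the percentages describe no feature of this cohort. That is correct. Group sizes, power and, for two factors, the number of levels are assumed. Patients needed only to be scheduled for at least ten sessions, so some may never reach the 60-session contrast used here. The figures show that the mechanism can be large, not how large it is here.

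What remains is more than missing detail: every subgroup comparison that the plan states is within a group.

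**Conclusion.** The point holds in a limited form. The stated subgroup comparisons validly describe within-group change but do not test whether change differs between groups, and the plan does not say that the information on this in its own fitted models is extracted or reported. If subgroups are compared by which contrasts are significant, equal true change gives discordant results in about 32% to 68% of cases under the assumed 80% power in the larger group and splits from 50/50 to 20/80. Other assumed powers give other values, and with no true change it is 2% for one contrast.

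A reader might go further and infer that the subgroup analysis is invalid or that the main result is in doubt. The documents do not support that: the overall-cohort analysis and the stated objectives are unaffected. This is a cheap improvement.

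**What to change.** For each factor and each PFT variable, report from the models already fitted:
- the joint group-by-timepoint interaction test;
- the between-group difference in change from baseline at each follow-up timepoint, with a 95% CI (27 differences with two levels per factor and three follow-ups: 3 × 3 × 3).

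Base any statement that subgroups differ, or do not differ, on these results. Keep the within-group changes as descriptive, with their CIs. Label the nine interaction tests as exploratory; adjusting them, for example by Holm, is an alternative.

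Interpret any difference as an association. The cohort is retrospective and its groups are not randomised: "All studied patients provided written consent to undergo HBOT (for a variety of clinical indications"). The section on the HBOT protocol gives two pressures without saying how patients came to receive one or the other, although it refers to a description elsewhere that may do so. The interaction test does not resolve confounding of this kind.

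The cost is a few extra contrasts and a sentence or two in the plan, with no new data. The downside is that fewer subgroup findings can be claimed, more so if the nine tests are adjusted, and some between-group intervals will be wide and must be reported as inconclusive.
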